Investigators: [name], MPH (University of Alabama at Birmingham, UAB); [name] (UAB); [name] [name] (UAB); [name], PhD (University of Nebraska Medical Center, UNMC); [name] (UNMC) [name] (KPSC); [name] (KPSC); [name] (KPSC)

Methodology: Open-label two-year cluster-randomized, parallel group, protocol-driven large pragmatic multicenter usual care-controlled trial designed to assess a highly automated, scalable, pharmacist-led intervention to optimize allopurinol treatment in gout.

3 Background

Gout is the most common form of inflammatory arthritis, affecting up to 8 million individuals in the US¹. Characterized by painful episodes of arthritis, gout results in substantial morbidity, physical disability, and reduced survival²⁻⁵. Contrary to other forms of arthritis, gout pathogenesis is well understood, with signs and symptoms resulting from inflammatory responses triggered by monosodium urate crystal deposition in joints or surrounding soft tissues. Under normal physiologic conditions, this occurs when serum urate (SU) concentrations exceed 6.8 mg/dl⁶.

Recognizing the role of hyperuricemia as the primary pathophysiologic culprit urate-lowering therapy (ULT) represents a cornerstone in gout management⁶. Allopurinol the most frequently prescribed first-line ULT is both efficacious and well tolerated in most patients. Despite this, allopurinol use is frequently accompanied by suboptimal patient outcomes that stem, in part, from inadequate prescribing practices and poor adherence⁷⁻¹³. For gout patients initiating allopurinol, management guidelines endorse gradual dose escalation to achieve a target SU goal^{14,15}. These recommendations are based on evidence that achieving and maintaining SU concentrations below 6.0 mg/dl greatly reduces the long-term risk of gout flares^{14,16}. Contrary to best practices promoted by these guidelines, the vast majority of patients initiating allopurinol in “real world” healthcare settings fail to undergo requisite SU assessment following initiation and only a small minority ever receive dose increases^{10,17,18}. In previous reports, only one in three gout patients initiating allopurinol ever received a dose increase and only a small fraction of these (~10%) ever received a daily dose exceeding 300 mg, dosing typically required to achieve desired SU concentrations and control of gout symptoms^{10,19}.

To address and potentially overcome barriers in achieving outcomes with allopurinol treatment, we completed the Randomized Evaluation of an Ambulatory Care Pharmacist-Led Intervention to Optimize Urate Lowering Pathways (RAMP-UP) study. RAMP-UP is a large pragmatic site-randomized trial designed to assess a highly automated, scalable, pharmacist-led intervention to optimize allopurinol treatment in gout.

4 Rationale for the Study

This project fits the UAB CORT in Gout and Hyperuricemia theme of “from bench to bedside, bedside into the community, and back again,” by proposing a novel Type 2 translational research project that addresses a currently unanswered question in gout, namely, how to effectively implement evidence into clinical populations.

4.1 Burden of Gout

Gout is a chronic and progressive form of arthritis occurring as a result of monosodium urate deposition in the joints and surrounding tissues. Chronic hyperuricemia is a necessary, although not sufficient, precursor of gout. It is estimated that gouty arthritis affects > 8 million people in the US alone,²⁰ now recognized as the most common form of inflammatory arthritis. Accompanying increased rates of disease risk factors including hypertension, renal insufficiency, and increased use of predisposing medications, gout incidence has risen two-fold in recent decades.^{21,22} Approximately two-thirds of gout patients will experience progressive disease and declines in physical function over time if left untreated.^{23,24} Recent studies show that gout is associated with work absenteeism and losses in work productivity.⁴ With an aging population, the burden posed by gout

will only continue to grow. Despite its extremely well known pathogenesis and the availability of highly efficacious therapies, gout continues to lead to considerable morbidity and mortality due to poor management and limited therapeutic adherence. Our translational research study will address this deficit in evidence implementation.

4.2 Urate Lowering Therapy (ULT) as the Cornerstone of Treating Chronic Gout

The treatment of chronic gout is based primarily on the use of ULT to reduce the frequency of, and eventually eliminate, acute flares in addition to reducing the risk of progressive joint destruction.²³ There are currently four ULT agents approved for the treatment of gout in the US including probenecid (a uricosuric), pegloticase (a biologic therapy approved for treatment-refractory gout), allopurinol, and febuxostat. Allopurinol and febuxostat work through the inhibition of xanthine oxidase, the rate limiting enzyme in endogenous urate production. A well-accepted goal of ULT administration in gout is to lower and maintain serum urate concentrations below 6.0 mg/dl, a concentration at which urate is more soluble and far less likely to form monosodium urate crystals that serve as a nidus for gouty inflammation. Achieving a serum urate of < 6.0 mg/dl with ULT leads to several clinical benefits in gout including decreased flare rates and dissolution of tophi.²⁵⁻²⁷ The target serum urate threshold of < 6.0 mg/dl has been adopted as a primary outcome in recent randomized controlled trials comparing febuxostat with allopurinol^{25,27,28} and has been endorsed as a goal of ULT administration in recently published international gout treatment guidelines.²⁹

4.3 Allopurinol: the Most Commonly Administered ULT in Gout

Available for more than 40 years, allopurinol remains the most frequently prescribed ULT, accounting for ~99% of all ULT prescriptions (Section C.1.1)). In contrast to probenecid, allopurinol can be dosed once daily (vs. twice to three times daily for probenecid), is effective in patients who overproduce and in patients who under-excrete uric acid (whereas probenecid is effective only in under-excretors), and may be effective in the context of significant renal insufficiency (whereas probenecid is not).³⁰⁻³² Febuxostat, a novel non-purine inhibitor of xanthine oxidase, also appears to have potent urate lowering effects at approved doses and may represent an important alternative in patients intolerant to allopurinol.^{25,27,28} While adverse events occur with allopurinol administration, these events appear to be uncommon with less than 5% of patients intolerant to the drug.³³ At present, febuxostat prescriptions represent only a small proportion of total ULT prescriptions in gout. With daily drug costs 20- to 40-fold higher than allopurinol (www.drugstore.com, accessed June 16, 2011), the precise role that febuxostat will play in cost-effective gout management remains unknown.

4.4 Gout Outcomes with Allopurinol Use

Many early studies confirmed the robust urate lowering effect of allopurinol, a treatment also yielding ample improvements in long-term outcomes including a reduction in gouty flares.^{25-28,31,34-37} A recent 28-week randomized trial examining fixed dose daily allopurinol revealed a 34% reduction in serum urate concentrations vs. a decrease of 3-4% for those receiving placebo.^{25,27,28} In a separate study, allopurinol in a fixed daily dose of 300mg was associated with a significant 50% reduction in tophus area.²⁵ Recent trials of allopurinol with more limited study durations (range of 4 to 12 months) have shown no significant declines in flare rates compared to the pre-trial period,^{25,27} a beneficial effect that appears to require up to 2 years of effective ULT.²⁵ To date, published studies examining the long-term impact of ULT on health-related quality of life, physical functioning, pain, and other patient reported outcomes are scarce, a knowledge deficit that will be addressed in Aim 1 of the current proposal. In addition to decreasing uric acid concentration, reducing tophus size and deposition, and reducing or eliminating acute flares, allopurinol use may be associated with other health benefits. Hyperuricemia is independently associated with cardiovascular morbidity and mortality.³⁸⁻⁴¹ In a placebo-controlled study of pediatric essential hypertension *led by our collaborator ([name], PhD)*, allopurinol use resulted in significant, albeit modest, declines in blood pressure.⁴² Xanthine oxidase inhibition via allopurinol has been shown to improve endothelial function, improving measures of both local and systemic blood flow⁴³ and been associated with improvements in renal function,^{44,45} physiological effects that will be the focus of Project 2 of this CORT application. In a retrospective study of over 9,000 US veterans with hyperuricemia, allopurinol administration was associated with a significant 22% reduction in all-cause mortality, that the authors speculated relates to protective cardiovascular effects.⁴⁶

4.5 Barriers to Optimal Allopurinol Use

Although approved at daily doses as high as 800 mg, allopurinol is rarely given at daily doses exceeding 300 mg. In one study, 97% of gout patients treated with allopurinol received doses of 300 mg/d or less (Figure 1).⁴⁷ It is well established that only a minority of patients achieve a target serum urate < 6.0 mg/dl with 'standard' dose allopurinol. Using a target serum urate threshold of < 5.0 mg/dl, investigators have shown that one-fourth of gout patients achieve this goal with 300 mg of daily allopurinol, a proportion that increases to 78% with a daily dose of 600 mg.⁴⁸ The limitation of 'standard' dose allopurinol has been borne out in recent clinical trials that have compared fixed daily doses of 300 mg to febuxostat. In those studies, ~40% of allopurinol treated gout patients achieved a final study urate level of < 6.0 mg/dl.^{25,27} Factors contributing to suboptimal allopurinol administration likely include, but are not limited to: 1) failure of prescribers to appropriately titrate allopurinol dose to achieve optimal serum urate target levels; 2) poor long term patient adherence to therapy; 3) drug intolerance, recognizing that this affects only a small proportion of patients;³³ 4) limited data regarding the effectiveness of doses exceeding 300 mg/day; and 5) concerns

[figure not shown]

Figure 1: Daily allopurinol dose use among patients with gout prescribed allopurinol; 97% with daily doses of ≤ 300 mg (Sarawate CA et al. Mayo Clin Proc 2006)

regarding increased toxicity with higher doses, particularly in the context of chronic kidney disease (CKD). It is important to note that despite common misconceptions, allopurinol administration has never been associated with deterioration in renal function in patients with renal impairment. Indeed, at least one small study has shown that allopurinol use may actually retard the progression of CKD.⁴⁵ In addition to unfounded concerns over potential deleterious effects on kidney function, results from a single case series of 78 patients suggested that 'higher dose' allopurinol may increase the risk of allopurinol hypersensitivity syndrome (AHS), an uncommon (0.1% to 0.4%) but serious drug related adverse event that appeared to be heightened in the context of CKD. These results led directly to the generation and promulgation of non-evidence based dosing guidelines that were founded on the relationship of renal function with observed oxypurinol concentrations (an allopurinol metabolite).⁴⁹ It is important to note that the 'effectiveness' of these guidelines in preventing AHS has not been demonstrated.⁵⁰ Indeed, many patients with CKD have developed AHS even with 'appropriately' dosed allopurinol.^{51,52} In their review of 120 gout patients receiving allopurinol, more than half (57%) required daily doses above the 'renal threshold' recommended by Hande to achieve target urate goals. In this study, only 1 patient developed AHS, a patient with normal renal function receiving 300 mg per day.⁵³ In a recent study of 90 gout patients, Stamp and colleagues found that increasing the dose of allopurinol above the thresholds proposed by Hande led to significant reductions in serum urate without increased toxicity.⁵⁴ Independent guidelines from both the European League Against Rheumatism (EULAR) and the British Society for Rheumatology have recommended that allopurinol dosing should be gradually increased to doses as high as 800 to 900 mg/day with a goal of achieving and maintaining serum urate concentrations below either 6.0 mg/dl or 5.0 mg/dl, respectively, recognizing the need for initial dose adjustments in the context of renal insufficiency.^{29,55} Current practice that adheres strictly to the Hande dosing guidelines⁴⁹ contrasts starkly with expert recommendations of judicious dose escalation accompanied by appropriate surveillance to achieve a target serum urate goal of < 6.0 mg/dl.⁵⁰

Without implementation of evidence into practice, the public health benefits of basic and clinical research cannot be realized. Yet, evidence has been notoriously difficult to implement across virtually all medical conditions, including gout. Discovering novel methods to implement evidence and conducting scientifically rigorous trials to test these methods has become an important area of research featured in this proposal. The Institute of Medicine (IOM) defines Type 2 (T2) translational (evidence implementation) research as research moving discovery from the bedside to community practice.⁵⁶ In gout, perhaps more than other musculoskeletal conditions, disease pathogenesis (including the central role of hyperuricemia) is well understood and highly effective therapies exist. The IOM has defined deficiencies in medical care as the "quality chasm",⁵⁷ and we have highlighted that a gout quality chasm also exists.^{47,58-60} The existence of this quality chasm in gout

management underscores the urgent need for quality T2 translational research in gout. The proposed study represents the largest systematic T2 translational research study to date ever conducted in gout patients, examining the use of a highly novel intervention with the goal of improving not only processes of care but also patient outcomes. The implementation of evidence through transportable and innovative data-collection and chronic disease-management technologies holds the promise of improving care for a larger number of gout patients than is either practical or feasible with more 'traditional' approaches.

5 Research Strategy

5.1 Study Design

RAM-P-UP is a cluster-randomized, parallel group, usual care-controlled trial evaluating the impact of a novel pharmacist-led, protocol-driven intervention focused on facilitating sUA goal attainment among gout patients initiating allopurinol in the Kaiser Permanente Southern California health system (Fig. 1). The intervention uses system redesign and direct patient engagement to optimize gout care. The aim of the study is to develop and test a pharmacist-led intervention to improve patients' treatment adherence and increase the proportion achieving sUA goal ≤ 6.0 mg/dl, the two primary study outcomes. The intervention has been led by an ambulatory care pharmacist and delivered, in part, using an automated calling system to encourage appropriate laboratory testing, allopurinol dose titration as needed, and medication adherence. The intervention has been designed to supplement usual care in a highly scalable manner that would be generalizable to many healthcare systems. Fig. 2 provides an overview of the study timeline including protocol development steps, system-level communication efforts, patient enrollment, and outcome assessment. During 2013, an expert consensus panel meeting, site randomization and 10-week pilot study were completed. Additionally, stakeholder involvement began in early 2013 and will continue throughout the study.

5.2 Study Setting

Kaiser Permanente Southern California (KPSC), the setting for this study, is an integrated healthcare delivery system with over 4 million members. The system is comprised of 14 major medical centers that include over 200 medical offices. Of these offices, we identified 116 ambulatory clinics that prescribed allopurinol during a recent one-year period. Few primary care providers or pharmacists practice at multiple clinics and each site typically has its own dedicated outpatient pharmacy. KPSC membership reflects the demographics of the region, accounting for 15% of the area's population.⁶¹ Based on a preliminary study in this population, we estimate that 78% of study patients will be men and participants will have a mean \pm SD age of 60 ± 14 years and BMI of 31.5 ± 6.6 kg/m².⁶² Further, we estimate that approximately 40% will be white/non-Hispanic, 16% will be black/African American, 20% will be Hispanic and 23% will be Asian/Pacific Islander.⁶¹ Finally, we expect that approximately 40% will have chronic kidney disease (CKD) stage III/IV while the remainder will have kidney function of mild CKD (Stage II) or better.⁶² Membership in KPSC can be obtained through individual or family plans, Medicaid/Medi-Cal, Medicare or employers.⁶¹

6 Outcomes

6.1 Primary Outcome

[figure not shown]
Co-primary outcomes are allopurinol adherence during the first year of treatment and achievement of a target SU (< 6.0 mg/dl) at one year. Adherence will be assessed using pharmacy dispensing data to calculate the proportion of days covered (PDC) with adherence defined as a $PDC \geq 0.8$. The PDC has been endorsed as the preferred method for assessing medication adherence using pharmacy claims data. When multiple sUA values are available, we will use the value that is at least 7 days post-index and that is most proximate to one-year of follow-up. The proportion achieving sUA < 6.0 mg/dl at one year will be examined in an additional subgroup analysis limited to adherent patients ($PDC \geq 0.8$). The effect of treatment assignment on primary outcomes will be evaluated in a separate subgroup analysis of "completers", defined as intervention patients responding to at least one IVR-administered survey.

Figure 1. Parallel group design for intervention and usual care patients. The RAmP-UP Study is an ongoing two-year cluster-randomized, parallel group, usual care-controlled trial evaluating the impact of a novel pharmacist-led, protocol-driven intervention focused on facilitating sUA goal attainment among gout patients initiating allopurinol in the Kaiser Permanente Southern California health system; sUA = serum urate; IVRS = interactive voice response system.

Intervention

Usual Care

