7.2 Exclusion Criteria

- In the absence of consensus surrounding optimal gout management, patients with advanced chronic kidney disease (CKD state V) were excluded.
- Pre-intervention provider and/or patient opt-out

*Incident prescription was defined by at least 12 months of previous membership in the absence of such a prescription.

8 Informed Consent (IC) Procedures

The study has been approved by the University of Alabama at Birmingham Institutional Review Board and will be conducted in accordance with the Declaration of Helsinki and the guidelines for Good Clinical Practice. Because the study was deemed to be a quality improvement project, a waiver of written informed consent was granted by the IRB allowing for the opt-out study design.

9 Study Procedures, Intervention, and Assessments

All study visits and procedures will be performed in facilities in the Kaiser Permanente Southern California Network.

Following initial allopurinol receipt (index date), prescribed and dosed at the discretion of the primary provider, pharmacist management will be provided to patients from intervention sites. Following a gout management algorithm that was produced through expert consensus⁶³, we developed the intervention to supplement usual care (UC). The algorithm incorporates a treat-to-target approach with the intervention delivered primarily through an interactive voice response system (IVR)⁶⁴. IVR messaging will be used to assess whether intervention patients continued to take prescribed ULT, alert patients regarding pending SU laboratory orders or prescription updates, and to provide encouragement. IVR messaging will be supplemented in select cases with telephone calls from the study pharmacist to provide more in-depth assistance (i.e. when patients report that they are not taking allopurinol) or respond to patient queries. Patients at non-intervention sites will receive only UC with the exception that patients without an sUA assessment in the previous 3 months (at both intervention and UC sites) will receive IVR reminders at baseline and after one- and two-years of follow-up to undergo laboratory testing.

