The number of IVRS calls made and successful contacts will be tracked and documented by the study pharmacist and research associate. The algorithm has been tailored to accommodate the slightly differing risk profiles of patients with normal kidney function or CKD stage I/II (Fig. 2a) and stage III/IV (Fig. 2b). In particular, the initial suggested dose increment of 50 mg/d represents the likelihood for CKD stage III/IV patients to start with 50 mg/d of allopurinol and escalate more slowly in order to reduce risks related to allopurinol hypersensitivity. For the same reason, the algorithm suggests that all dose escalation for CKD III/IV patients be done according to sUA measurements whereas those with stage II or better kidney function could be dose escalated to 300 mg/d without sUA measurements. This will allow the study pharmacist to reduce patient burden related to blood draws recognizing that at least 50% of patients are likely to need at least 300mg/d of allopurinol to achieve sUA < 6.0 mg/d.

The algorithm has a similar design for all levels of kidney function. After receiving an incident allopurinol fill, the study packet and IVRS reminders, all patients in the intervention will receive an adherence assessment IVRS message. If classified as non-adherent (took allopurinol as indicated on b5 day over the past week), the patient will receive a phone call with encouragement from the pharmacist followed by a repeat assessment. If the patient is adherent, they will receive an IVRS message notifying them that a blood draw is due. Following sUA measurement, patients with a sUA ≤ 6.0 mg/dl will receive the sUA goal achieved IVRS message while patients ≥ 6.0 mg/dl will receive allopurinol dose escalation and the corresponding IVRS dose adjustment message. An adherence assessment IVRS message will follow 2–4 weeks later. The sequence of dose escalation, adherence assessment and blood draw IVRS messages will continue until the patient achieves a sUA < 6.0 mg/dl.

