9.4 Patient interactions

Initial allopurinol dosing will be prescribed at the discretion of the primary gout provider. All patients meeting eligibility criteria will be randomized into either study arm, and mailed a study packet including an opt-out letter, baseline health survey and gout educational material. The opt-out letter will notify patients of the quality improvement program, and ask them to return a pre-addressed, postage-paid notification if they wish to opt-out of participation. The baseline health survey will record the presence and number of gout attacks in the past 3 months, patients' gout-specific health as measured on a 21-point visual analog scale and the 12-question Short Form Health Survey (SF-12). The same health survey will be sent via mail at the end of years 1 and 2. The gout educational material to be included in the mailing is produced by the Arthritis Foundation and covers a variety of topics including: gout as a chronic disease, typical treatment options used, and important lifestyle changes for self-management.

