All patients will be entered into the IVRS system to receive weekly IVRS reminders (maximum of 3) to return baseline questionnaires. The usual care patients will receive no further contact after these IVRS messages until the blood draw IVRS for the 1 year and 2 year outcomes. Intervention patients, by contrast, will continue into the gout care algorithm with the adherence assessment IVRS message. The study pharmacist will intervene further if the IVRS proves insufficient at any task for intervention patients. There were three primary indications where the IVRS may prove insufficient: 1) if the patient is unresponsive to IVRS calls or fails to show up for ordered labs or prescription fill pick-up; 2) a patient self-reports allopurinol non-adherence via IVRS; or 3) a patient calls the pharmacist directly. Direct telephone communications will be categorized into four broad categories: 1) introduction of IVRS and its purpose with the intent to improve use among unresponsive or confused participants, 2) gout education, 3) adherence reassessment and encouragement, and 4) dose adjustments. For gout education, a guide to frequently asked questions (FAQ) will be provided (Appendix A). Adherence reassessment and encouragement is designed to determine the extent of nonadherence, identify reasons for nonadherence and provide encouragement for improved adherence as appropriate. Finally, dose adjustments will be facilitated by the study pharmacist using live telephone calls if not accomplished by IVRS.

10 Data Management and Statistical Analyses

[name] of the UAB School of Public Health will oversee all data management and analysis for the proposed study. [name] and the study team at UAB will ensure that the data collected and analyzed for this study are of the highest quality possible, and updated as needed to guarantee high quality data through quality control and quality assurance. Edit checks will be reviewed by the statisticians, program manager, as well as other team members on an ongoing basis to evaluate whether any checks need to be added or any existing checks need to be modified. All data will be entered into and all analyses will be conducted using Statistical Analysis System (SAS; Cary, NC) Version 9.4 or higher.

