10.1 Sample Size Justification

Sample size estimates are based on an assumption that 30% of gout patients given allopurinol from usual care clinics will achieve a sUA below 6.0 mg/dl [1]. To be conservative, we assumed a worst-case scenario intra-class correlation coefficient of 0.1 by study site. Based on these assumptions, an alpha of 0.05 and 51 intervention sites, 11 patients per site (or 561 total patients from intervention sites) will provide 80% power to detect a 10% absolute improvement in sUA goal achievement (i.e. $\geq 40\%$ success rate) [25]. Finally, we estimate that after opt-out up to 20% of patients would drop-out or otherwise be nonresponsive to the study. We thus inflated the sample size estimate using a standard equation of the estimated sample size divided by 1 minus the estimated drop out proportion. Our target enrollment using this equation was over 702 per study arm; 1404 total.

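### The completers analysis in Section 6.1 promises an effect of treatment assignment in a group that only intervention patients can enter

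*Combined protocol and SAP*

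**What the plan says.** After the co-primary outcomes (adherence by PDC and sUA goal at one year), Section 6.1 announces a further analysis in a group that it names completers. Its aim is stated first: "The effect of treatment assignment on primary outcomes will be evaluated in a separate subgroup analysis of" that group. Membership is then restricted to one arm, the group being "defined as intervention patients responding to at least one IVR-administered survey".

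The procedures show who can receive such a survey.

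- Section 9 (opening text) ties the adherence check to one arm: "IVR messaging will be used to assess whether intervention patients continued to take prescribed ULT".
- Section 9.2 lists the adherence survey among the IVR message types of the gout care algorithm and says "all patients in the intervention will receive an adherence assessment IVRS message".
- Section 9.4 gives usual care up to three IVR reminders to return the baseline questionnaire, and then: "The usual care patients will receive no further contact after these IVRS messages until the blood draw IVRS". That later call serves the one- and two-year outcomes.
- The health survey used in both arms is on paper: "The same health survey will be sent via mail at the end of years 1 and 2" (Section 9.4).

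Section 10.3 specifies an intent-to-treat GEE analysis of the co-primary outcomes, with clustering by clinic and missing sUA counted as failure. It does not mention completers.

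**The concern.** An effect of assignment is a contrast between arms. The completer set contains one arm by definition, so the stated quantity does not exist in it. An analyst who follows the plan must choose a comparator that the plan does not name, and the obvious choice is the whole usual-care arm.

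That contrast removes unresponsive patients from one arm only. Responding is behaviour observed after randomisation and may be related to prognosis, so the contrast can differ from zero when the intervention does nothing. Nor does response mark receipt of the intervention: Section 9.4 has the pharmacist step in when a patient does not answer IVR calls, so non-completers may still be managed.

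What is at stake is the label. Section 14.6 requires the first publication to follow the analysis stipulated in the protocol. A comparison of responders with all usual care could therefore appear, for both co-primary outcomes, as a pre-specified effect of assignment.

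**Working it through.** **1. Can a usual-care patient be a completer?** The definition in 6.1 admits intervention patients only. The procedures agree: the IVR contacts in usual care are reminders (return the questionnaire, have blood drawn), and the questionnaire itself is mailed. The set holds no usual-care patients, so assignment does not vary in it. This step needs no arithmetic and no assumption.

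**2. Does 10.3 supply a comparator or estimator?** No. It describes only the intent-to-treat model for these outcomes, with no matching, weighting or complier-average method.

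**3. What would completers versus all usual care show under no effect?** The plan attaches no sample size or power to this analysis, so there is no figure to reproduce. What follows is an illustration.

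Inputs from the plan (Section 10.1):
- sUA success p = 0.30, applied to both arms because no effect is assumed
- ICC 0.1
- 702 patients per arm ("Our target enrollment using this equation was over 702 per study arm; 1404 total"; 561/0.8 = 701.25, rounded up to 702)
- 51 intervention sites

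Assumed, because the plan is silent:
- 51 usual-care sites
- response share r
- gap g (responder minus non-responder success)
- a two-sided 5% normal test

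Formulas:
- completer rate = p + g(1 − r); non-responder rate = p − gr; false difference = g(1 − r)
- design effect = 1 + (m − 1) × 0.1, where m is patients per site
- usual care: m = 702/51 = 13.76, design effect 2.28
- completers: n = 702r, design effect 2.14, 2.00 and 1.86 at r = 0.9, 0.8 and 0.7
- rejection = P(|Z| > 1.96), where Z has mean (difference/SE)

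Example, r = 0.8 and g = 0.20: completer rate 0.30 + 0.20 × 0.2 = 0.34. SE = √(0.34 × 0.66 × 2.00/561.6 + 0.30 × 0.70 × 2.28/702) = 0.0385. Difference/SE = 0.04/0.0385 = 1.04, and rejection is 0.180.

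| r | g (points) | Non-responders | Completers | False difference (points) | SE | Rejection |
|---|---|---|---|---|---|---|
| 0.9 | 10 | 21% | 31% | 1 | 0.0375 | 0.058 |
| 0.9 | 20 | 12% | 32% | 2 | 0.0377 | 0.083 |
| 0.9 | 30 | 3% | 33% | 3 | 0.0378 | 0.125 |
| 0.8 | 10 | 22% | 32% | 2 | 0.0382 | 0.082 |
| 0.8 | 20 | 14% | 34% | 4 | 0.0385 | 0.180 |
| 0.8 | 30 | 6% | 36% | 6 | 0.0388 | 0.340 |
| 0.7 | 10 | 23% | 33% | 3 | 0.0390 | 0.120 |
| 0.7 | 20 | 16% | 36% | 6 | 0.0394 | 0.331 |
| 0.7 | 30 | 9% | 39% | 9 | 0.0398 | 0.619 |

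With g = 0 the rejection rate is 0.050, as it should be. With the gap reversed (g = −10 points), the differences are −1, −2 and −3 points at r = 0.9, 0.8 and 0.7, with rejection 0.058, 0.083 and 0.125.

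With 561 per arm instead of 702, rejection at r = 0.8 is 0.079, 0.167 and 0.313 for gaps of 10, 20 and 30 points, so the choice of sample size matters little. For scale, the trial is designed to detect 10 points.

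**4. Direction.** An upward bias for sUA is plausible: unreachable patients may more often lack a follow-up value, and 10.3 counts them as failures. It is not assured. One of the stated triggers for a pharmacist call is that "a patient self-reports allopurinol non-adherence via IVRS", and a patient who does so has responded to the survey and is a completer. No PDC figure is given, because the plan states no planning rate for adherence.

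**The case against.** The strongest reply is that this is ordinary shorthand for a per-protocol style analysis. The trial has two arms, so engaged intervention patients would naturally be compared with usual care, and the fault shrinks to an unstated comparator and a loose label. That reading is plausible, but it does not rescue the analysis. Selecting on response in one arm only still does not give an effect of assignment.

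A second reply is that other contrasts are possible. All patients enter the IVR system for the baseline reminders, so an engagement measure common to both arms might be built, or a complier-average estimator used. Either would be a different definition from the one written and would need its own assumptions. Pharmacist contact with non-responders makes a simple complier-average rescaling hard to justify.

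Some criticism of the illustration stands. The 30-point gap implies success of only 3% to 9% among non-responders, so the top figures are extremes. The upward direction is also weakened for sUA: any value at least seven days after the index date can count, one-year laboratory reminders reach both arms, and the pharmacist follows up missed tests. The missing-sUA mechanism does not apply to PDC, which comes from dispensing data.

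Finally, this is a separate subgroup analysis on which no sample size or decision rule depends. That is correct and limits the severity.

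**Conclusion.** The concern holds. As written, the analysis cannot estimate what it names, and this conclusion rests on the documents alone. The nearest workable version, completers against all usual care, is open to selection bias of (1 − r) × g. Over the assumed positive gaps of 10 to 30 points, the false difference is 1–3 points at 90% response, 2–6 at 80% and 3–9 at 70%, with rejection of roughly 6–12%, 8–34% and 12–62% for a nominal 5% test. These sizes depend on an assumed response share, gap and usual-care site count, and the sign could reverse. The intent-to-treat primary analysis is sound on this point, so the change is one that should be made; it is not a threat to the trial's main result.

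A lesser, related point: the sUA analysis limited to patients with PDC ≥ 0.8, also in 6.1, has members in both arms but conditions on a co-primary outcome measured after randomisation. It too should not be read as a treatment effect.

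**What to change.** In Sections 6.1 and 10.3:

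1. State that the intent-to-treat analysis is the only estimate of the effect of treatment assignment.
2. Delete the claim that the completers analysis evaluates an effect of assignment.
3. Report completer outcomes descriptively within the intervention arm, with no between-arm treatment-effect test.
4. Report the sUA proportions among adherent patients descriptively as well.

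The cost is a few sentences of wording and no new data. The completers analysis loses its treatment-effect claim, but the information on engagement is kept.
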